The primary study outcomes for **Aims 2-4** are the claims-based measures of asthma medication use, outcomes, and OOP costs listed below, measured at the individual level. Our project focuses on these patient-centered, clinically-relevant outcomes (RQ-6), and will not focus on total costs to employers and the health care system.

1. Adherence to controller medications (Aims 2-3): We will assess adherence to guideline-recommended asthma controller medications, including ICS, LTA, or ICS-LABA, which have been shown to reduce asthma morbidity and adverse outcomes. These medications are subject to the deductible in HSA-HDHPs without PDLs, free in HSA-

HDHPs with PDLs, and subject to copayments in traditional plans. We will measure: 1) PDC, the proportion of days that members have their medication available per month. Proportion of days covered is calculated based on the days' supply in each pharmacy fill, spread over the days following the fill. Previous studies have used proportion of days covered as a valid measure of adherence that is associated with better clinical outcomes (IR-4). 2) medication discontinuation, defined as experiencing a gap of more than 60 days in availability of a controller medication following a period of at least 180 days of continuous treatment (i.e. with no gap in availability greater than 60 days). Claims-based measures such as these have been shown to be valid measures of adherence (IR-4).

Because PDLs are not standardized nationally, there is some variation among health plans in the specific types of drugs included. From a review of several other insurers' and employers' PDLs, those that include asthma medications cover both controllers and beta agonists/rescue medications. However, some of these PDLs include a few less commonly used inhaled corticosteroids which are not included in the PDL that we propose to study. To address this variation, in addition to measuring adherence to asthma controller medications generally, we will also measure adherence to the specific controller medications included in the PDL and adherence to the sub-set of controller medications that are not included in the PDL (Aerospan, Arnuity ellipta, Asmanex HFA, Aerobid, Azmacort).

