2. **Use of asthma rescue medications (Aims 2-3):** We will assess use of albuterol and levalbuterol inhalers, the primary asthma rescue medications prescribed to patients, which are subject to the deductible in HSA-HDHPs without PDLs, free in HDHPs with PDLs, and subject to copayments in traditional plans. All albuterol and levalbuterol inhalers are brand-name drugs containing 200 puffs each. We will exclude nebulized versions as these are predominantly used by younger children and do not come in standardized doses. As in our prior study, we will measure the standardized number of inhalers dispensed per month based on National Drug Code (NDC) in pharmacy claims. Given the inter-relationship between rescue and controller medication use, we will also measure the ratio of controller medications to total asthma medications, a metric for which higher values are associated with better asthma control and lower rates of asthma-related ED visits.
3. **Use of spacers and nebulizer machines (Aims 2-4):** Based on input from patients and stakeholders, and with additional input from questions from added questions in the qualitative interview guide in response, we will assess changes in the number of spacers and nebulizer machines received by study patients, based on claims data. We will measure changes in receipt of spacers and nebulizer machines after a switch to an HSA-HDHP vs. remaining in a traditional plan to see if changes in the cost-sharing for these devices leads to a decrease in receipt and an increase in OOP costs to families.
4. **Asthma-related ED visits and hospitalizations (Aims 2-3):** As a measure of potentially avoidable short-term complications, we will measure asthma-related ED visits and hospitalizations that have a primary ICD-10 diagnosis code for asthma.
5. **OOP health care costs (Aim 4):** We will calculate consumer price index (CPI)-adjusted OOP costs for asthma medications and other health services, summing deductible, co-pay, and coinsurance amounts, aggregated into annual measures. Financial burden due to OOP costs will be defined as annual family OOP costs as a percent of family income, with cutpoints of >5% and >10% to indicate financially burdensome OOP costs.

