## **Predictors and Covariates**

Table 2 shows the main predictors and covariates we will use in the proposed study for propensity matching to create study cohorts (CI-1, 4-5), predicting or adjusting outcomes, or stratifying analyses. Our primary predictor variables include study period and insurance type. Study period indicates the one-year period before or up to three years after the index date. Insurance type includes: 1) HSA-HDHP without PDL; 2), HSA-HDHP with PDL; and 3) traditional plan.

Other co-variates include asthma severity in the baseline period using the HEDIS definition for persistent asthma (see above under Study Population), and using chronic oral corticosteroid therapy (180+ days in the prior year) or any use of omalizumab in the baseline year to define severe asthma. To estimate co-morbidity, we will use the well-established Johns Hopkins Adjusted Clinical Groups (ACG) scores which use ICD-10 codes in the baseline period to calculate a standardized morbidity score in a specified time period. We will measure the presence of other chronic conditions from claims data in the baseline year using the Johns Hopkins ACG system. We will also measure whether enrollees have COPD as a co-morbidity, as there can be overlap with COPD and asthma, and use of similar medications.

A unique innovation of our study is the availability of data linkages (IR-2) with consumer data from a

major credit reporting company linked to insurance claims from our data vendor, Optum. Consumer data elements include total household income, net

worth, and race/ethnicity. We will combine self-reported race/ethnicity data from credit card and loan applications with data from Optum on surname analysis for identifying Hispanic or Asian ethnic groups and geocoding to derive race/ethnicity from census data. We will also use census-based indicators for neighborhood education and poverty levels. Other variables used to propensity-match cohorts and adjust for confounding will include sex and age; state/region of residence; individual versus family plan; baseline number of outpatient visits, presence of an inpatient hospitalization, and total expenditures; employer size (number of employees); and average employer baseline expenditures per capita (CI-1, 4-5).

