We will begin by performing descriptive analysis using the full dataset of all enrollees with asthma and their family members to examine predictors and trends over time concerning insurance coverage type, asthma care utilization, and costs for asthma care. Then among the targeted study groups, we will compare baseline characteristics between study groups using chi-square, t-tests, and Poisson or quantile regression. We will next display each outcome as a monthly time series of rates or counts, comparing trends over time in the groups of interest. We will use both ITS and DiD frameworks for analyses. Presuming our matching approach will generate similar baseline trends in the intervention and control groups, we will use ITS to display results and DiD to convey effect estimates in a more intuitive manner than ITS estimates. Controlling for potential confounders, we will use generalized linear models (GLMs) to model the independent effect of switching to each of the two types of HSA-HDHPs (with or without PDLs) on the likelihood of each outcome, assessed by interacting insurance type and study period variables in models. Data from the same patients in successive years are correlated, as are data from individuals from the same family. Extended GLMs - generalized estimating equations (GEE) and generalized linear mixed models (GLMM) - are appropriate methods to adjust for this correlation and to examine changes in outcomes between baseline and follow-up.

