For analyses of rescue medication use, we will focus on albuterol and levalbuterol inhaler users. We will limit the time period of interest to 2009-2017, as albuterol inhalers, the primary asthma rescue medication, became available only as higher-priced branded CFC-free medications as of 2009 due to the FDA ban on generic CFC-containing inhalers. The standardized number of rescue inhalers dispensed will be modeled as count data in difference-in-differences models. ITS models will be used to model changes in level and trend of monthly rates of rescue inhalers dispensed, as in our previous study. Because use of controller medications can affect need for rescue medications, we will add controller medication adherence as a co-variate; sub-analyses will stratify by controller medication use in the baseline period. We will also model the ratio of controller medications to total asthma medications. For analyses of asthma-related ED visits and hospitalizations, outcomes can be binary, counts, or continuous. We will use logistic GEE models to estimate the effect of switching to each type of HSA-HDHP on binary outcomes such as any asthma-related hospitalization. We will use negative binomial regression to model the effect for count outcomes such as ED visits. We will select the conditional mean and variance functions based on the actual data, using a log link with a Gamma error distribution. To inform final model specification, we will employ specification tests including the Pregibon Link test for non-linearity and a modified Park test to select the conditional variance function.

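### The rescue-inhaler models add controller adherence without saying when it is measured; if post-switch values are used, they would not estimate the overall effect that Aim 2 seeks.

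*Combined protocol and SAP*

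**What the plan says.** The Aim 2 part of the Analysis plan sets out two rescue-inhaler models. For the first, "The standardized number of rescue inhalers dispensed will be modeled as count data in difference-in-differences models". The second is an interrupted time-series (ITS) model of monthly dispensing rates. It then states: "Because use of controller medications can affect need for rescue medications, we will add controller medication adherence as a co-variate". The rest of that sentence reads "sub-analyses will stratify by controller medication use in the baseline period", and this is the only mention of timing.

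Other sections bear on the reading:
- **Target.** The general modelling paragraph for Aim 2 promises generalized linear models "to model the independent effect of switching to each of the two types of HSA-HDHPs (with or without PDLs) on the likelihood of each outcome", through an interaction of insurance type and study period. It names no adherence term. Aim 2 in the Specific Aims asks for the impact of the plans on both controller and rescue medication use.
- **Adherence as an outcome.** The Outcomes section lists controller adherence first among the Aims 2-4 outcomes and measures it as "PDC, the proportion of days that members have their medication available per month". Values therefore exist both before and after the switch.
- **Adherence as an intermediate.** The Conceptual Model has higher cost-sharing lowering controller adherence, and poorer adherence raising the need for rescue medication. For a PDL both steps run the other way.
- **Covariates.** Table 2 has no row for controller adherence. Its medication row is a baseline-year count.

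**The concern.** A covariate in a difference-in-differences (DiD) model should not itself be changed by the intervention if the interaction term is to carry the overall effect. The Aim 2 hypothesis and the Hypothesized Effect Size section both expect the plan switch to change controller adherence. If the monthly post-switch values enter the rescue model, the interaction loses some or all of the effect that runs through adherence. It is also open to bias from changing asthma severity, which can drive controller and rescue fills together. The result is neither the overall effect that Aim 2 asks for nor a declared direct effect.

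Rescue use is listed under the primary study outcomes for Aims 2-4, although it is not one of the three outcomes powered in Table 3. The Limitations section already allows for a null result on inhaler use. A reader could not interpret such a null without knowing whether it was adjusted for post-switch adherence. Aim 3 reuses the modelling strategy, so its adult/child and family contrasts would carry the same ambiguity. The PDC, emergency department/hospitalization and out-of-pocket cost models are not affected.

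**Working it through.** The plan gives no effect size or power figure for rescue inhalers, so there is no stated figure to reproduce. The check has three parts.

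**1. Does the text fix the timing?** No.
- For concurrent adherence: the stated reason (controller use affects need for rescue medication) fits it, PDC is monthly, and the baseline wording is attached only to the strata.
- For baseline adherence: the section on Predictors and Covariates says "Other co-variates include asthma severity in the baseline period using the HEDIS definition for persistent asthma", matching uses baseline values, and the Analysis plan describes adjustment as control of confounding.
- Neither set settles it, since adherence itself is not in Table 2.

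**2. What would each choice do?** Write log overall rate ratio = log direct rate ratio + b × ΔPDC, where b is the change in log rescue rate per unit of PDC. Adding concurrent PDC moves the log interaction by about −(fitted slope) × ΔPDC.

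A Poisson DiD simulation of a switch without a PDL used an assumed direct rate ratio of 0.95, ΔPDC = −9 points and b = −1.0. The estimated rate ratio was:

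| Adherence term | Rate ratio |
|---|---|
| None | 1.03 |
| Baseline PDC | 1.03 |
| Concurrent PDC | 0.95 |

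With b = −0.5 the three values were 0.99, 0.99 and 0.95.

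A second simulation set the direct effect to zero and let PDC measure adherence with error (ΔPDC = −9 points, b = −1.0, PDC standard deviation 0.25 assumed). The interaction was +9.3% with no covariate and +9.3% with baseline PDC. With concurrent PDC it was 0.0%, +1.8%, +3.5% and +4.5% at reliability 1.0, 0.8, 0.6 and 0.5. The 0.0% follows from the set-up. Baseline PDC leaves the overall effect intact, while concurrent PDC removes a share about equal to its reliability.

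**3. How large might the removed part be?** This is purely illustrative.
- From the documents: a 5-9% fall in PDC without a PDL, 1-4% more fills with one (both from Hypothesized Effect Size), and baseline PDC 46% (Table 3 footnote).
- Assumed: b from −0.25 to −1.0; reliability r from 0.5 to 1.0; PDC rises in proportion to fills.
- Formula: part removed = exp(r × b × ΔPDC) − 1.

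The plan does not say whether 5-9% is relative or absolute, so both readings are shown.
- Without a PDL, relative: 0.46 × 5% = 2.3 points and 0.46 × 9% = 4.14 points. Smallest: exp(0.5 × 0.25 × 0.023) − 1 = +0.29%. Largest: exp(1.0 × 1.0 × 0.0414) − 1 = +4.23%.
- Without a PDL, absolute: exp(0.5 × 0.25 × 0.05) − 1 = +0.63% to exp(0.09) − 1 = +9.42%.
- With a PDL: 0.46 × 1% = 0.46 points and 0.46 × 4% = 1.84 points, giving exp(−0.5 × 0.25 × 0.0046) − 1 = −0.06% to exp(−0.0184) − 1 = −1.82%.

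**Direction.** With a negative fitted slope, −(−0.5)(−0.09) = −0.045 on the log scale, so the estimate moves toward lower rescue use without a PDL. With a positive fitted slope of, say, +0.25, −(0.25)(−0.09) = +0.0225, and the movement reverses. Worsening severity that raises both kinds of fill pushes the fitted slope upward.

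**The case against.** The strongest reply is that baseline adherence is what the authors mean. The plan's other clinical covariates are baseline measures, all models are to adjust for key Table 2 predictors to control confounding, and the Table 2 controller count is for the baseline year. The stated reason fits baseline confounding as well as it fits concurrent adherence. This stands as a possible reading, and on it nothing is wrong. It does not settle the matter, because adherence is not a Table 2 row and the sentence itself gives no timing.

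A second reply is that results without the covariate are already planned. Each outcome will be displayed as a monthly series by group, and adherence is said to be added after the DiD and ITS models are described. The series is descriptive, however, and the word for adding does not make an unadjusted model the main one. The plan also says "we will also measure the ratio of controller medications to total asthma medications", but a ratio does not give the effect on inhalers dispensed. The baseline strata leave the specification of the main model open.

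A third reply concerns size, and it largely stands. Slope, reliability and PDC spread are all assumed. The Study Population section includes intermittent asthma, and rescue users who are not on controllers have little adherence to lose, so the upper figures are probably high.

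A reader might also infer that adjustment must shift the estimate toward lower rescue use without a PDL and higher use with one, or that it would reverse the sign. The documents do not support this. The direction follows only if the fitted slope is negative, as the Conceptual Model implies, and confounding by changing severity could weaken or reverse it. The move from 1.03 to 0.95 above is one assumed case.

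**Conclusion.** The point holds in conditional form. The plan leaves the timing of the adherence covariate open and names no main rescue-inhaler model without post-switch adherence. If post-switch adherence is used, the insurance type by period term does not estimate the overall impact on rescue use that Aim 2 seeks, and Aim 3 inherits this. If baseline adherence is used, the problem does not arise. It would go too far to say that the plan does adjust away the effect, since the text permits that reading without requiring it.

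Direction and size are not established. The illustrative ranges rest wholly on assumed negative slopes and assumed reliabilities. They suggest that the PDL contrast is little affected and that the contrast without a PDL matters more. This should be fixed before analysis because the better specification is clear and costs nothing. Confidence is medium, given the open timing.

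**What to change.** In the rescue-medication paragraph of the Aim 2 analysis plan:
- exclude post-switch controller adherence from the main rescue-inhaler DiD and ITS models, and adjust for baseline-year PDC only, if at all;
- name that specification as the main rescue analysis;
- label any model with concurrent adherence as an exploratory direct-effect or mediation analysis.

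State that the same rule applies to the Aim 3 models that reuse this strategy. If baseline adherence was always intended, saying so is enough. The cost is one or two sentences, with no new data.

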### A. BACKGROUND

**Asthma is a major cause of preventable disease burden (PCORI Methodology Standard RQ-3).** More than 25 million people in the U.S. have asthma, including 8% of adults and 9% of children, with significant racial and income disparities in prevalence. Morbidity from asthma is substantial, causing 10.5 million healthcare visits, 479,000 hospitalizations, and 3,100 deaths in 2009. Low income and racial/ethnic minority patients are more likely to experience adverse outcomes, leading to four times as many hospitalizations and five times as many deaths in blacks than whites, and this gap has been increasing. Guidelines recommend controller medications such as inhaled corticosteroids (ICS), leukotriene antagonists (LTA), or combination ICS and long-acting  $\beta_2$ -agonists (LABA) that are proven to improve asthma control and quality of life, prevent exacerbations, and reduce need for oral corticosteroids, emergency department (ED) visits, hospitalizations, and deaths due to asthma. However, many patients do not use daily controller medications, with 14-20% of individuals not filling prescribed controller medications once. Poor adherence to asthma controller medications increases the risk for adverse clinical outcomes. Increased levels of cost-sharing for asthma medications that lead to reduced adherence have also been associated with adverse downstream outcomes such as increased rates of asthma exacerbations, oral steroid bursts, and asthma-related ED visits and hospitalizations.

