*Hypothesis (see Figure 2): Enrollees with asthma in HSA-HDHPs without PDLs will have worse adherence to controller medications, greater need for rescue medications, and higher rates of asthma-related ED visits and hospitalizations, with widening of income and racial/ethnic disparities; the addition of a PDL will improve use of controllers and rescue medications, reduce ED and hospitalization rates, and lessen disparities.*

Analyses will compare changes in outcomes from baseline to up to three years of follow-up among 1) asthma patients switched to HSA-HDHPs without PDLs from traditional plans vs. matched patients whose employers remain in traditional plans; and 2) patients switched to HSA-HDHPs with PDLs from traditional plans vs. matched controls remaining in HSA-HDHPs without PDLs. Sensitivity analyses will compare patients switched to HSA-HDHPs with PDLs from traditional plans vs. those who remain in traditional plans to examine the combined impact of both increasing the deductible and gaining a PDL. We will use separate regression models to compare year-to-year changes for each intervention group relative to its matched control group, rather than including all patients in a single model with multiple interaction terms. For secondary analyses of enrollees in the larger set of plan types that include PDLs, we will compare enrollees who are switched from plans with no PDL to plans with a PDL vs. those who remain in plans without a PDL. These analyses will match and adjust for different baseline plan types and deductible levels.

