Asthma controller medications are intended to be taken regularly, so we will examine controller medication adherence using ITS. We will test the statistical significance of level or trend changes following insurance plan type switch using GLM models, adjusting for seasonality and first-order autocorrelation between sequential monthly measurements using the empirical sandwich estimator. Our analytic model will compare the odds ratio of having the primary therapy in the category available each day before and after the coverage switch. Our key independent variables will be: month, period (before or after the benefit switch), and month after the plan switch, adjusting for the same covariates as above. In addition to modeling changes in adherence to controller medications generally, we will address the variation across health plans in the types of controller medications included in PDLs by conducting sub-analyses to examine changes in adherence to the specific controller medications that are included in the PDL and those that are not included in the PDL (Aerospan, Arnuity ellipta, Asmanex HFA, Aerobid, Azmacort). For patients using medications that are not included in the PDL, we will examine the degree to which patients change to medications that are included on the PDL.

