In all statistical models, we will include key individual-level predictors from Table 2 to adjust for potential confounding. To determine the impact of HSA-HDHP with and without PDLs on vulnerable populations (RQ-4) and test for heterogeneity of treatment effects among vulnerable populations (HT-1-4), we will first perform stratified analyses, comparing outcomes between intervention and control subgroups defined by the binary measures of the risk factors of interest (low income, minority race/ethnicity, moderate-severe asthma, presence of other chronic conditions (including co-morbid diagnosis of COPD; we will also conduct analyses limited to ages 4-50 to remove the effect of COPD co-morbid diagnoses), high ACG morbidity). We hypothesize that these vulnerable subgroups will have worse adherence, more frequent adverse clinical outcomes, and higher OOP costs. We will use three-way interaction terms (insurance type \* study period \* subgroup) to test for statistical differences between subgroups in the impact of the change to an HSA-HDHP with PDL vs. remaining in a traditional plan. Heterogeneity of treatment effect analyses for these key variables will be reported along with overall findings from the combined population. Given that we will be conducting sub-group analyses to test for heterogeneity of treatment effect based on race/ethnicity and income using three-way interaction terms, we elected to separate the analyses of heterogeneity of treatment effect by age group into Aim 3 (described below), rather than add a fourth interaction term to the analyses in Aim 2. In Aim 2 analyses, we will include

both adults and children together, with age included as a co-variate. Given that health plan cost-sharing policies in HSA-HDHPs and PDLs usually apply across enrollees regardless of age, and given that health plans, employers, policy makers, and families must make decisions about HSA-HDHPs and PDLs for both adults and children together, we felt it was important to evaluate the impact at the overall population level.

**Aim 3:** to examine the extent to which the response to HSA-HDHPs and PDLs is affected by the presence of other family members with asthma or other chronic conditions.

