**Table 3: Power calculations**

| Contrast of Interest                                  |                                 | Least detectable absolute difference |          |
|---|---------------------------------|--------------------------------------|----------|
| Intervention Group                                    | Control                         | Overall                              | Children |
| Controller medication adherence (PDC)*         |                                 |                                      |          |
| HSA-HDHP with PDL (n=4,222)                           | HSA-HDHP without PDL (n=16,888) | 2.0%                                 | 3.5%     |
| HSA-HDHP without PDL (n=18,000)                       | Traditional plan (n=72,000)     | 1.0%                                 | 1.7%     |
| Asthma related ED visits or hospitalizations** |                                 |                                      |          |
| HSA-HDHP with PDL (n=4,222)                           | HSA-HDHP without PDL (n=16,888) | 1.2%                                 | 2.0%     |
| HSA-HDHP without PDL (n=18,000)                       | Traditional plan (n=72,000)     | 0.6%                                 | 1.0%     |
| OOP costs***                                   |                                 |                                      |          |
| HSA-HDHP with PDL (n=4,222)                           | HSA-HDHP without PDL (n=16,888) | \$47                                 | \$80     |
| HSA-HDHP without PDL (n=18,000)                       | Traditional plan (n=72,000)     | \$23                                 | \$40     |

\*Baseline rate estimated at 46% \*\* Baseline rate estimated at 8.4 per 100 patients with asthma \*\*\*Baseline OOP costs estimated at \$740 based on data from current studies in the same data set.

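### Aim 2 tests disparities only through relative effects, so for ED visits and hospitalizations the test can be null, or point below 1, while the absolute gap widens

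*Combined protocol and SAP*

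**What the plan says.** All references are to the combined protocol and SAP, section C (Approach), unless noted.

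- **Hypothesis (Analysis plan, Aim 2).** Moving to an HSA-HDHP without a PDL is expected to worsen outcomes "with widening of income and racial/ethnic disparities"; adding a PDL is expected to lessen them. Whether a disparity is a difference or a ratio is not stated.
- **Test (Aim 2, heterogeneity of treatment effect).** Stratified analyses by binary risk factors come first. Three-way interaction terms are then used "to test for statistical differences between subgroups in the impact of the change"; the contrast named there is the switch to a plan with a PDL against staying in traditional coverage. The same paragraph expects the vulnerable subgroups to have worse adherence and more adverse outcomes.
- **Models (Aim 2).** For hospitalization: "We will use logistic GEE models to estimate the effect of switching to each type of HSA-HDHP on binary outcomes". For ED visits: "We will use negative binomial regression to model the effect for count outcomes such as ED visits". The text then refers to a log link with Gamma errors and to choosing the mean and variance functions from the data. For controller adherence: "Our analytic model will compare the odds ratio of having the primary therapy in the category available each day"; this describes the interrupted time-series model.
- **What is absent.** No section defines an additive-scale interaction, a difference in model-predicted rates between subgroups, or an interval for the change in a gap.

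**The concern.** In a logistic or log-link model, the three-way coefficient is a ratio of odds ratios or of rate ratios. Its null hypothesis is that the plan switch multiplies the odds or rate by the same factor in both subgroups. If one subgroup starts higher, the same factor adds more events there, so the gap in events per 100 patients grows although the null is exactly true. Slightly different factors can make the two scales disagree in direction.

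Unequal starting levels are what the plan itself expects, so this is not a corner case. At stake is what the study may conclude about vulnerable patients. Employers and insurers could be told that no widening was found while the excess of ED visits or admissions among low-income or minority patients had grown. The issue is the same whichever plan contrast the interaction is applied to.

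**Working it through.** **Plan's own figures.** The plan gives no figure for this test, so there is none to reproduce. Table 3 supplies a baseline of 8.4 ED visits or hospitalizations per 100 and group sizes of 18,000 vs 72,000 and 4,222 vs 16,888. No subgroup rates are given.

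**Assumptions.** One third of patients are vulnerable (V) and two thirds are not (N). Controls do not change. The negative binomial model has its usual log link. Baseline rates are 6.4 (N) and 12.4 (V) per 100; check: 6.4 × 2/3 + 12.4 × 1/3 = 4.27 + 4.13 = 8.4.

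**Formulas.** With baselines b and rate ratios r:

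- interaction = r_V / r_N
- change in absolute gap = b_V(r_V − 1) − b_N(r_N − 1)

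| Case | r_N, r_V | Rates after switch (N, V) | Gap, from 6.0 | Interaction |
|---|---|---|---|---|
| Common effect | 1.20, 1.20 | 7.68, 14.88 | 7.20 | 1.00 |
| Opposite direction | 1.25, 1.20 | 8.00, 14.88 | 6.88 | 0.96 |
| PDL direction | 0.80, 0.85 | 5.12, 10.54 | 5.42 | 1.06 |

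In the third case the gap narrows while the interaction points to relative widening.

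**Zone of disagreement.** The gap widens when r_V > 1 + (b_N/b_V)(r_N − 1). For r_N = 1.20 this is 1 + (6.4/12.4)(0.20) = 1.103. Any r_V between 1.103 and 1.20 widens the gap with an interaction below 1.

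**Range.** Take baseline pairs from 7.4/10.4 to 5.6/14.0 (each averaging 8.4) and common rate ratios of 1.1 to 1.3. The widening at an interaction of exactly 1.00 runs from 3.0 × 0.1 = 0.3 to 8.4 × 0.3 = 2.5 per 100.

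**Logistic model.** At assumed risks of 2% and 4%, a common odds ratio of 1.25 gives 2.49% and 4.95%. The gap goes from 2.00 to 2.46 points; the ratio of odds ratios is 1.00.

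**PDC.** Table 3 gives a 46% baseline. The hypothesised 5-9% decrease is read here as percentage points. A drop from 46% to 41% is an odds ratio of (0.41/0.59)/(0.46/0.54) = 0.816. Applied to assumed subgroup values of 49% and 40%, it gives 43.9% and 35.2%, so the gap moves from 9.0 to 8.7. Over the assumed pairs tried, for drops of 5 to 9 points, the gap changes by −1.8 to +0.7 points, mostly a slight narrowing.

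**Precision.** For the common-effect case at 18,000 vs 72,000, assume Poisson events and independent pre and post periods. The variance of the absolute three-way difference is the sum of rate/N over the eight cells:

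- (0.064 + 0.0768)/12,000 + (0.064 + 0.064)/48,000 + (0.124 + 0.1488)/6,000 + (0.124 + 0.124)/24,000 = 0.0000702, so SE = 0.84 per 100.
- z = 1.20/0.838 = 1.43, which gives power of about 30% at two-sided 5%. With dispersion 1 (variance = mean + mean²) it is about 27%.
- The ratio interaction rejects 5% of the time, since its null is true.
- The difference detectable with 80% power is about 2.80 × 0.84 = 2.3 per 100, or 2.5 with dispersion 1.
- At 4,222 vs 16,888 the SE grows by √(18,000/4,222) = 2.06 to 1.73, and power falls to about 11%.

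For assumed rates of 1.5 and 6.0 per 100 (hospitalization alone) and a common rate ratio of 1.15, the gap goes from 4.5 to 1.15 × 4.5 = 5.175. Power of the absolute contrast in the larger comparison is about 24%.

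**The case against.** The strongest reply is that the plan never says disparity means an absolute gap. Its background expresses disparity as a ratio: "four times as many hospitalizations and five times as many deaths in blacks than whites". On that reading a ratio interaction is a coherent test and 0.96 is a true relative narrowing. This stands. A reader might infer that the planned test is wrong, or that an interaction below 1 is a false narrowing; the documents do not support either. They support only that the scale is unnamed and that model choice settles it by default.

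Other points that stand:

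- A reader might carry the fourfold figure into the cohort. It is national background on black and white patients. The cohort is commercially insured, and the tested subgroups are binary, including low income and pooled minority race/ethnicity.
- A reader might see Table 3, headed "Least detectable absolute difference", as contradicting the ratio test. It covers only overall and child comparisons and powers no income or race interaction, so it shows no mismatch.
- An estimate near 0.96 would seldom be significant (about 8% power in the larger comparison). The likelier error is a null result read as no widening, rather than a declared narrowing.
- The absolute test would itself usually miss the widenings illustrated.

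What does not stand is that existing steps already cover this. Stratified results, monthly rate displays and difference-in-differences summaries might let a reader derive absolute changes. None specifies the scale of the subgroup contrast or an interval for the change in the gap.

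**Conclusion.** The concern holds as an omission that should be closed before analysis, for asthma-related ED visits and hospitalizations. The planned interaction answers whether relative effects differ; it cannot by itself answer whether the gap in events grew. Under assumed baselines consistent with 8.4 per 100, common rate ratios of 1.1 to 1.3 leave 0.3 to 2.5 per 100 of widening at an interaction of 1.00, and modestly unequal ratios reverse the direction.

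That the scales can diverge is exact algebra. The sizes rest on assumed subgroup rates, a one-third vulnerable share and unchanged controls; the power figures also rest on the assumed event distribution and pre/post independence. For PDC near 46% the divergence is small and varies in sign, and the link for the annual PDC models is not stated, so the point should not be pressed there. Nothing here shows that the ratio interaction should be dropped or demoted.

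**What to change.** Add to the Aim 2 heterogeneity paragraph that disparity change for ED visits and hospitalizations will be reported on both scales:

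1. From each fitted model, predict the mean for every arm × period × subgroup cell, averaging over a stated covariate distribution.
2. Report the three-way difference in events per 100 patients, with a delta-method or cluster-bootstrap confidence interval that keeps repeated years and family members together.
3. Show it beside the ratio interaction, and state that a null ratio interaction will not be read as no widening.

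The cost is a sentence or two in the SAP and a post-estimation step; no new data are needed. The absolute contrast keeps its meaning whichever link the data-driven model checks select. The drawback is its imprecision, so present it as an estimate with its interval rather than as a decisive test.
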